### **Renal Biomarkers**

Selected renal biomarkers, including retinol binding protein and beta-2-microglobulin, will be summarized by treatment arm and visit using descriptive statistics. The difference in change from baseline in these biomarkers at Week 48 between 2 treatment arms will be tested using the Wilcoxon rank-sum test.

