# 3.2. Study Design Rationale

### Control, Blinding, Randomization and Stratification

A bPI in combination with 2 NRTIs, an established regimen for treatment-naïve HIV-infected patients, is the active control treatment in this study. The active control treatment consists of the DRV/COBI FDC (PREZCOBIX/REZOLSTA) coadministered with FTC/TDF FDC (TVD). In addition, since TAF is substituted by TDF in the comparator treatment, the active control treatment will allow a direct comparison of these 2 ARVs for safety assessments.

Blinded treatment will be used to reduce potential bias during data collection and evaluation of clinical endpoints.

Randomization will be used to minimize bias in the assignment of subjects to treatment arms, to increase the likelihood that known and unknown subject attributes (eg, demographic or baseline characteristics) are evenly balanced across treatment arms, and to enhance the validity of statistical comparisons across treatment arms. Equal randomization will be done because this requires a lower total sample size to attain the same power versus randomization with unequal division.

Two stratification factors (HIV-1 RNA level [ $\leq$ 100,000 copies/mL or >100,000 copies/mL] and CD4+ cell count [<200 cells/ $\mu$ L or  $\geq$ 200 cells/ $\mu$ L] at screening) will be applied in the randomization process and will subsequently be used in the statistical analysis as covariates in the models. Since previous publications have shown that baseline viral load can be a predictive factor for outcome, this will ensure a balanced distribution of subjects across treatment arms.  $^{11,15}$ 

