## 11.3. Sample Size Determination

A sample size of 670 (335 subjects in D/C/F/TAF arm and 335 subjects in the control arm) will yield 90% power. It is assumed that both treatment arms have a response rate of 80% (HIV-1 RNA <50 copies/mL at Week 48 as defined by the FDA snapshot analysis), that the noninferiority margin is 10%, and that the significance level of the test is at a 1-sided, 0.025 level.

A minimum of 170 subjects (85 per treatment arm) is targeted to be included in the bone investigation substudy. Assuming a 4% inter-subject variability in BMD and a 1-sided alpha level of 2.5%, 85 subjects per treatment arm is sufficient to detect at least an absolute difference of 2% between the treatment arms with 90% power. Power calculations are presented in Table 5.

	Mean % Change from Baseline	Common Standard Deviation (%)	Power
N=170	2	3.5	96%
		4	90%
	3	3.5	>99%
		4	>99%

 Table 5:
 BMD at the Lumbar Spine, Power Calculations

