## **Serum Creatinine and Cystatin C**

The changes from baseline in serum creatinine, eGFRcreatinine (by Cockcroft-Gault and by CKD-EPI) and eGFRcystatin (by CKPD-EPI) at Weeks 48 and 96 will be summarized by treatment arm and using descriptive statistics. The difference in changes from baseline at Week 48 in serum creatinine between the 2 treatment arms will be tested using ANCOVA, including baseline serum creatinine in the model.

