## **DXA Substudy – Bone Investigations**

Baseline, post-baseline, and the percent change from baseline at Weeks 24, 48, and 96 for selected bone biomarkers, including CTX, P1NP, PTH and 25-hydroxy vitamin D, will be summarized by treatment arm and visit using descriptive statistics. The within-treatment comparison will be done using the Wilcoxon signed-rank test. The comparison between the 2 treatment arms at Weeks 24 and 48 will be performed using the Wilcoxon rank-sum test.

Percent change from baseline in spine and hip BMD at Weeks 24, 48, and 96, as well as the change from baseline in BMD T-score will be summarized by treatment arm and visit using descriptive statistics. The between-treatment differences at Weeks 24 and 48 will be estimated using ANCOVA model, including baseline BMD value and other clinically relevant factors (if deemed necessary) in the model. The within-treatment comparison will be done using a paired t-test. A supportive longitudinal repeated measures analysis will be performed on this endpoint to obtain an estimate of the between-treatment difference along with its 95% CI at Week 48. This model will include post-baseline percent change from baseline as a response variable, terms for treatment, visit, the interaction of visit and treatment and the corresponding baseline BMD value as a covariate and other clinically relevant factors (if deemed necessary). An unstructured covariance matrix will be used to model the correlation among repeated measurements.

The BMD T-score will be summarized descriptively. BMD status based on the T-score (normal: ≥-1; osteopenia: from <-1 to -2.5; osteoporosis: <-2.5) will be tabulated.

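### The renal and bone biomarker comparisons use a rank-sum test with no adjustment for baseline: valid, but possibly inefficient, and the protocol names no between-arm estimate with an interval

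*Protocol*

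**What the plan says.** Protocol 11.6, Renal Biomarkers, takes the change from baseline to Week 48 in markers including retinol binding protein and beta-2-microglobulin, and says that the difference "between 2 treatment arms will be tested using the Wilcoxon rank-sum test".

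Protocol 11.6, DXA Substudy – Bone Investigations, lists as summaries "Baseline, post-baseline, and the percent change from baseline at Weeks 24, 48, and 96 for selected bone biomarkers" and then states: "The comparison between the 2 treatment arms at Weeks 24 and 48 will be performed using the Wilcoxon rank-sum test". The natural reading is that the rank-sum test is applied to percent change. The endpoint list in Protocol 11.1 speaks only of change.

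Neither paragraph names a baseline covariate, the randomisation strata, or an estimated difference with an interval. The synopsis repeats both.

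Three neighbouring continuous endpoints are adjusted for baseline. The change in serum creatinine "will be tested using ANCOVA, including baseline serum creatinine in the model". CD4+ count (11.4.2) and BMD (11.6) also use ANCOVA with the baseline value. CD4+ gets a 95% CI, and BMD gets one from its supportive repeated-measures model. Protocol 3.2 says that the two stratification factors "will subsequently be used in the statistical analysis as covariates in the models".

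The SAP supplied covers Week 96 only. It treats renal and bone biomarkers descriptively (SAP 5.2.3.2 and 5.4.2) and makes no between-arm test of them.

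**The concern.** Protocol 1.5.1 gives a lower potential for renal and bone toxicity as a reason for using TAF, and Protocol 3.2 says that the control arm allows a direct safety comparison of TAF with TDF. Change in renal biomarkers and in bone biomarkers at Week 48 are stated objectives. Control subjects move to D/C/F/TAF after unblinding, so the randomised comparison of these markers is essentially the double-blind one.

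A change score carries all the noise of the baseline measurement. When baseline and follow-up are only moderately correlated, regression on baseline leaves less residual variance than subtracting it. A rank-sum p-value also does not say how large the difference is, which is what a reader of a tubular or bone-turnover marker wants to know.

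**Working it through.** **The plan's own power figures.** None is stated for any biomarker. The two that are stated reproduce.
- Main study: "A sample size of 670 (335 subjects in D/C/F/TAF arm and 335 subjects in the control arm) will yield 90% power", with 80% response in both arms, a 10% margin and a one-sided 0.025 level. n per arm = (1.960 + 1.282)² × 2 × 0.8 × 0.2 / 0.10² ≈ 337, against 335 stated. Power at 335 is 89.9%.
- BMD: 85 per arm, difference 2%, SD 4%, one-sided 2.5%. Φ(2 / (4 × √(2/85)) − 1.960) = Φ(1.30) = 90.3%, against 90% stated.

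**Analytic comparison, normal data.** Let ρ be the correlation of baseline with follow-up, with equal variances σ². A change score has variance 2σ²(1 − ρ); ANCOVA leaves σ²(1 − ρ²). The efficiency of change against ANCOVA is therefore (1 + ρ)/2. The rank-sum test multiplies this by 3/π = 0.955. Setting ANCOVA power at 90% (two-sided 5%), power on change is Φ(3.242 × √efficiency − 1.960):

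| ρ | (1+ρ)/2 | × 3/π | Wilcoxon power | Sample-size inflation |
|---|---|---|---|---|
| 0.3 | 0.65 | 0.621 | 72% | 1.61 |
| 0.5 | 0.75 | 0.716 | 78% | 1.40 |
| 0.7 | 0.85 | 0.812 | 83% | 1.23 |
| 0.9 | 0.95 | 0.907 | 87% | 1.10 |

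**Simulation, skewed data.** Every input here is an assumption, because the documents give no SD, correlation or effect for any biomarker. The log marker is normal with equal SD at both times, and one arm is lowered by 0.2 log units (a ratio of e^−0.2 = 0.82). Tests are two-sided at 5%. Renal: log SD 1, 300 per arm, Wilcoxon on change. Bone: log SD 0.5, 85 per arm, Wilcoxon on percent change. Power, planned Wilcoxon v rank ANCOVA:

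| ρ | Renal | Bone |
|---|---|---|
| 0.3 | 45 v 72% | 60 v 76% |
| 0.5 | 55 v 78% | 70 v 81% |
| 0.7 | 78 v 92% | 89 v 93% |
| 0.85 | 96 v 99% | no gain |

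Repeat runs agree within about 4 points. Log-scale ANCOVA is slightly ahead of rank ANCOVA (renal 71, 82 and 93% at ρ 0.3, 0.5 and 0.7). With no true effect, all these tests reject in about 4 to 6% of trials.

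**Why not raw-scale ANCOVA.** With log-normal data, 335 per arm, ρ = 0.7 and log-scale ANCOVA near 90%, Wilcoxon on change has 74% against 70% for raw-scale ANCOVA at log SD 0.8, and 73% against 51% at log SD 1.2. Copying the creatinine model unchanged could lose power.

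**What the strata add.** If they explain a share R² of the residual variance, leaving them out lowers 90% to Φ(3.242 × √(1 − R²) − 1.960): 89.7% at R² = 1%, 88.5% at 5%, 86.8% at 10%.

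**The case against.** A rank test is a sensible choice for skewed markers, and randomisation makes the unadjusted version valid. That stands in full. So does the point that using ANCOVA for creatinine and BMD does not make a different method for skewed markers inconsistent.

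A reader might infer more than the documents support:
- *That the test ignores baseline.* It does not: it analyses change or percent change. Only the covariate adjustment is absent.
- *That much of the power is lost.* The documents cannot show this. The gap closes at high correlation. It also closes for larger effects: with a 0.4 log-unit effect in the renal setting, Wilcoxon on change already reaches 95, 98 and 99.9% at ρ 0.3, 0.5 and 0.7. Percent change ranks subjects as the log ratio does, so renal figures must not be carried over to bone.
- *That leaving out the strata is a serious conflict with Protocol 3.2.* That section speaks of covariates in models, and a rank-sum test has none. The creatinine, CD4+ and BMD analyses do not name the strata either, and their likely contribution is small.
- *That bone safety rests on these markers.* BMD is the powered substudy endpoint and is baseline-adjusted.
- *That the plan has no effect estimate at all.* Protocol section 11 is a general description that defers detail to the SAP, and the SAP supplied covers Week 96. The gap is established for the protocol only.

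What survives is narrower: an adjusted analysis uses data already collected, holds the type I error, and in these settings was never materially less powerful.

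**Conclusion.** The point holds as a cheap improvement to consider, not as an error. No stated figure is wrong, and these are secondary or substudy endpoints with no power claim. Under the assumptions above, the gain from rank ANCOVA is about 27, 23 and 14 points for renal markers at correlations 0.3, 0.5 and 0.7 (72 − 45, 78 − 55, 92 − 78), falling to about 3 at 0.85. For bone markers it is about 16, 11 and 4 points, then none. These sizes rest wholly on assumed log SDs, correlations and one effect size. The value of an estimate with an interval does not depend on those inputs.

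**What to change.** For both marker sets, make the between-arm comparison baseline-adjusted: either rank ANCOVA (ranks of the follow-up value on ranks of baseline, with treatment) or ANCOVA on the log scale, but not ANCOVA on the raw scale. Adding the two randomisation strata is optional and would bring these analyses into line with Protocol 3.2. Report the geometric mean ratio with its 95% CI from the log-scale ANCOVA, and keep the Wilcoxon test as a sensitivity analysis. State which scale, change or percent change, the bone comparison uses.

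The cost is analysis wording and one extra model; no new data, visits or subjects are needed. If the Week 48 analysis has already been run, as the wording of the Week 96 SAP implies, add the adjusted analysis and label it supplementary.

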#### **ECG**

ECG assessments were done locally, only at screening and thus not suitable to be analyzed. For definitions of abnormalities of ECG, refer to Attachment 5.

## **Vital Signs**

Descriptive statistics of vital sign (pulse rate, systolic and diastolic blood pressure) values and changes from baseline will be summarized at each scheduled time point. The percentage of subjects with values beyond clinically important limits will be summarized. For definitions of abnormalities of vital signs, refer to Attachment 5.

#### **Physical Examination**

Descriptive statistics of changes from baseline will be summarized at each scheduled time point.

## **DXA Substudy – Bone Investigations**

Baseline, post-baseline, and the percent change from baseline at Weeks 24, 48, and 96 for selected bone biomarkers, including CTX, P1NP, PTH and 25-hydroxy vitamin D, will be summarized by treatment arm and visit using descriptive statistics. The within-treatment comparison will be done using the Wilcoxon signed-rank test. The comparison between the 2 treatment arms at Weeks 24 and 48 will be performed using the Wilcoxon rank-sum test.

Percent change from baseline in spine and hip BMD at Weeks 24, 48, and 96, as well as the change from baseline in BMD T-score will be summarized by treatment arm and visit using descriptive statistics. The between-treatment differences at Weeks 24 and 48 will be estimated using ANCOVA model, including baseline BMD value and other clinically relevant factors (if deemed necessary) in the model. The within-treatment comparison will be done using a paired t-test. A supportive longitudinal repeated measures analysis will be performed on this endpoint to obtain an estimate of the between-treatment difference along with its 95% CI at Week 48. This model will include post-baseline percent change from baseline as a response variable, terms for treatment, visit, the interaction of visit and treatment and the corresponding baseline BMD value as a covariate and other clinically relevant factors (if deemed necessary). An unstructured covariance matrix will be used to model the correlation among repeated measurements.

The BMD T-score will be summarized descriptively. BMD status based on the T-score (normal: ≥-1; osteopenia: from <-1 to -2.5; osteoporosis: <-2.5) will be tabulated.

#### 11.7. Treatment Adherence

Treatment adherence based on pill count will be summarized by means of descriptive statistics and frequency tabulations.

## 11.8. Data Monitoring Committee

An independent DMC will be established to monitor the safety and efficacy information to ensure the safety of the subjects enrolled in this study, and to allow regular assessment of the risk/benefit profile of the applied therapy schemes. The details will be provided in a separate DMC charter.

A formal futility analysis for lack of (non-inferior) efficacy of the D/C/F/TAF regimen will be performed, using a conditional power approach, ie, probability of claiming non-inferiority at the completion of the study based on the available interim data. To this end, the available Week 24 data (used as predictor for the primary endpoint), and the Week 48 primary endpoint data (if any) will be used. Further details regarding the derivation of the conditional power and the choice of threshold for the conditional power to stop for futility will be provided in the DMC charter and DMC statistical analysis plan. The futility analysis will be guided by the DMC, and the sponsor and study team will remain blinded. It is not the intention to stop the study early in case of superiority or noninferiority of the D/C/F/TAF regimen versus the control group.

In addition, a blinded sample size re-estimation procedure will be applied to allow for an adjustment in sample size to maintain adequate power in case the overall response rate is anticipated to be different than assumed, eg, due to a higher drop-out rate. Details will be provided in the DMC charter.

The DMC will consist of 2 external medical experts in the relevant therapeutic area and 1 external statistician. The DMC responsibilities, authorities, and procedures will be documented in its charter.

#### 12. ADVERSE EVENT REPORTING

Timely, accurate, and complete reporting and analysis of safety information from clinical studies are crucial for the protection of subjects, investigators, and the sponsor, and are mandated by regulatory agencies worldwide. The sponsor has established Standard Operating Procedures in conformity with regulatory requirements worldwide to ensure appropriate reporting of safety information; all clinical studies conducted by the sponsor or its affiliates will be conducted in accordance with those procedures.

#### 12.1. Definitions

#### 12.1.1. Adverse Event Definitions and Classifications

#### **Adverse Event**

An AE is any untoward medical occurrence in a clinical study subject administered a medicinal (investigational or non-investigational) product. An AE does not necessarily have a causal relationship with the treatment. An AE can therefore be any unfavorable and unintended sign (including an abnormal finding), symptom, or disease temporally associated with the use of a

medicinal (investigational or non-investigational) product, whether or not related to that medicinal (investigational or non-investigational) product. (Definition per ICH).

This includes any occurrence that is new in onset or aggravated in severity or frequency from the baseline condition, or abnormal results of diagnostic procedures, including laboratory test abnormalities.

Note: The sponsor collects AEs starting with the signing of the ICF (refer to Section 12.4.1, All Adverse Events, for time of last AE recording).

An AE does not include the following (see also Section 12.3 and 12.4.3):

- Medical or surgical procedures if the condition that leads to the procedure is an AE.
- Pre-existing diseases or conditions or laboratory abnormalities present or detected before the screening visit that do not worsen; any medical condition or clinically significant laboratory abnormality with an onset date before the ICF is signed, is not an AE. It is considered to be pre-existing and should be documented in the medical history eCRF.
- Situations where no untoward medical occurrence has occurred (eg, hospitalization for elective surgery, social and/or convenience admissions).
- Overdose without clinical sequelae.
- Uncomplicated pregnancy.

## **Serious Adverse Event**

An SAE based on ICH and EU Guidelines on Pharmacovigilance for Medicinal Products for Human Use is any untoward medical occurrence that at any dose:

- Results in death; however, death is an outcome of an AE, and not an AE in itself.
- Is life-threatening (The subject was at risk of death at the time of the event. It does not refer to an event that hypothetically might have caused death if it were more severe.)
- Requires inpatient hospitalization or prolongation of existing hospitalization.
- Results in persistent or significant disability/incapacity.
- Is a congenital anomaly/birth defect.
- Is a suspected transmission of any infectious agent via a medicinal product.
- Is Medically Important\*
  - \*Medical and scientific judgment should be exercised in deciding whether expedited reporting is also appropriate in other situations, such as important medical events that may not be immediately life threatening or result in death or hospitalization but may jeopardize the subject or may require intervention to prevent one of the other outcomes listed in the

definition above. These should usually be considered serious. These should usually be considered serious. Examples of such events are:

- Intensive treatment in an emergency room or at home for allergic bronchospasm.
- Blood dyscrasias or convulsions that do not result in hospitalization.
- Development of drug dependency or drug abuse.

If a serious and unexpected AE occurs for which there is evidence suggesting a causal relationship between the study drug and the event (eg, death from anaphylaxis), the event must be reported as a serious and unexpected suspected adverse reaction even if it is a component of the study endpoint (eg, all-cause mortality).

## Additional clarification on AEs/SAEs:

- Complications that occur during hospitalizations are AEs. If a complication prolongs the hospitalization, it is an SAE.
- In-patient hospitalization means the subject has been formally admitted to a hospital for medical reasons, for any length of time; this may or may not be overnight. It does not include presentation or care within an emergency department.
- The investigator should attempt to establish diagnosis of an event on the basis of signs, symptoms and/or other clinical information; in such cases, the diagnosis should be documented as the AE and/or SAE and not the individual signs/symptoms.
- A distinction should be made between seriousness and severity of an AE. An AE that is assessed as grade 4 (potentially life-threatening) should not be confused with an SAE. Severity is a category utilized for rating the intensity of an event, and both AEs and SAEs can be assessed as grade 4. An event is defined as 'severe' when it meets the predefined criteria as described the DAIDS toxicity grading table in Attachment 1 (see also Section 12.1.3).

#### Unlisted (Unexpected) Adverse Event/Reference Safety Information

An AE is considered unlisted if the nature or severity is not consistent with the applicable product reference safety information at the time the AE is reported.

For D/C/F/TAF FDC tablet, the expectedness of an AE will be determined by whether or not it is listed in the adverse reaction table provided in the IB or its relevant IB addendum.  For DRV/COBI FDC and FTC/TDF FDC used in the control arm, the expectedness of an AE will be determined by whether or not it is listed in the applicable USPI current at the time the AE is reported.

## Adverse Event Associated With the Use of the Drug

An AE is considered associated with the use of the drug if the attribution is possible, probable, or very likely by the definitions listed in Section 12.1.2.

#### 12.1.2. Attribution Definitions

#### **Not Related**

An AE that is not related to the use of the drug.

#### Doubtful

An AE for which an alternative explanation is more likely, eg, concomitant drug(s), concomitant disease(s), or the relationship in time suggests that a causal relationship is unlikely.

#### **Possible**

An AE that might be due to the use of the drug. An alternative explanation, eg, concomitant drug(s), concomitant disease(s), is inconclusive. The relationship in time is reasonable; therefore, the causal relationship cannot be excluded.

#### **Probable**

An AE that might be due to the use of the drug. The relationship in time is suggestive (eg, confirmed by dechallenge). An alternative explanation is less likely, eg, concomitant drug(s), concomitant disease(s).

